8.5.1.4. Treatment of Outliers in Pharmacokinetic Analysis

If a value is considered to be anomalous due to being inconsistent with the expected PK profile, it may be appropriate to exclude the value from the PK analysis. However, the exclusion of any data must have strong justification and will be documented in the CSR.

Any quantifiable predose concentration value on the first dosing day of all parts of the study will be considered treated as 0 for the PK analysis. The PK parameters from any such profile will be listed but excluded from descriptive statistics and statistical analysis.

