3.1.3. Part C (Drug-Drug Interaction Study)

Part C will comprise an open-label, fixed-sequence, enrolling healthy male subjects to investigate the effect of multiple oral doses of itraconazole on the single oral dose PK of CCI in healthy subjects. There will be 1 group; Group C1, consisting of 12 male subjects. Part C will start after completion of blinded safety, tolerability, and PK data review in Part A. All subjects will receive each of the following treatments:

- Days 1 and 11: single oral dose of KRP-A218
- Day 4: 2 \times single oral doses of 200 mg itraconazole, approximately 12 hours apart
- Days 5 to 13: single oral doses of 200 mg itraconazole

The study days of dosing of itraconazole and KRP-A218 may be amended to extend the interval between the first dose of KRP-A218 and the first dose of itraconazole depending on the observed $t_{1/2}$ of CCI.

Potential subjects will be screened to assess their eligibility to enter the study within 28 days prior to the first dose administration. Subjects will be admitted into the study site on Day -1 and be confined to the study site until discharge on Day 14.

Subjects will return to the study site for a follow-up visit 7 to 10 days after the last dose of KRP-A218. The follow-up period may be extended depending on the observed $t_{1/2}$ of CCI.

[figure not shown]
Based on the ongoing review of the safety, tolerability, and PK results, additional nonresidential visits may be required. The number of additional visits per subject will not exceed 3 and will not extend beyond 28 days after each final dosing occasion. All subjects may stay in the CRU even outside treatment period due to COVID-19 risks.

The dietary state for dosing of KRP-A218 alone on Day 1 and KRP-A218 co-administered with itraconazole on Day 11 will be determined by comparing the PK data between fed and fasted state in Group A2a. Itraconazole on Days 4 to 10, 12 and 13 will be administered in the fasted state. The dose level of KRP-A218 will be confirmed based on the available safety, tolerability, and PK data in preceding Parts A and/or B of the study.

An overview of the study design is shown in [Figure 4](#), and the planned dose levels in [Figure 5](#).

[figure not shown]
A Schedule of Assessments is presented in [Appendix 6](#).

Figure 4: Study Schematic (Part C)

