4.3. Part C (Drug-Drug Interaction Study)

Part C will comprise an open-label, fixed-sequence, enrolling healthy male subjects to investigate the effect of multiple oral doses of itraconazole on the single oral dose PK of [CCI](#) in healthy subjects. There will be 1 group; Group C1, consisting of 12 male subjects. Part C will start after completion of blinded safety, tolerability, and PK data review in Part A. All subjects will receive each of the following treatments:

- Days 1 and 11: single oral dose of KRP-A218
- Day 4: 2 \times single oral doses of 200 mg itraconazole, approximately 12 hours apart
- Days 5 to 13: single oral doses of 200 mg itraconazole

The study days of dosing of itraconazole and KRP-A218 may be amended to extend the interval between the first dose of KRP-A218 and the first dose of itraconazole depending on the observed $t_{1/2}$ of [CCI](#)

Potential subjects will be screened to assess their eligibility to enter the study within 28 days prior to the first dose administration. Subjects will be admitted into the study site on Day -1 and be confined to the study site until discharge on Day 14.

Subjects will return to the study site for a follow-up visit 7 to 10 days after the last dose of KRP-A218. The follow-up period may be extended depending on the observed $t_{1/2}$ of [CCI](#)

Based on the ongoing review of the safety, tolerability, and PK results, additional nonresidential visits may be required. The number of additional visits per subject will not

[figure not shown]
exceed 3 and will not extend beyond 28 days after each final dosing occasion. All subjects may stay in the CRU even outside treatment period due to COVID-19 risks.

The dietary state for dosing of KRP-A218 alone on Day 1 and KRP-A218 co-administered with itraconazole on Day 11 will be determined by comparing the PK data between fed and fasted state in Group A2a. Itraconazole on Days 4 to 10, 12 and 13 will be administered in the fasted state. The dose level of KRP-A218 will be confirmed based on the available safety, tolerability, and PK data in preceding Parts A and/or B of the study.

The total duration of study participation for each subject (from screening through follow-up visit) is anticipated to be up to 49 days.

[figure not shown]
An overview of the study design is shown in [Figure 4](#), and the planned dose levels in [Figure 5](#).

Figure 4: Study Schematic (Part C)

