8.5.1.2. Criteria for Calculation and Reporting of Area Under the Concentration-time Curve

The minimum requirement for the calculation of AUC will be the inclusion of at least 3 consecutive concentrations above the lower limit of quantification. If there are only 3 consecutive concentrations, at least 1 should follow C_{max} . An exception may be made for metabolites, where C_{max} may be the last timepoint.

If the extrapolated area is $> 20\%$, $AUC_{0-\infty}$ (and derived parameters) may be excluded from the summary statistics and statistical analysis at the discretion of the sponsor or pharmacokineticist.

If $AUC_{0-\infty}$ cannot be determined reliably for all subjects and/or dose levels/treatments, an alternative AUC measure, such as AUC to a fixed timepoint or $AUC_{0-t_{last}}$, may be used in the statistical analysis of dose proportionality/food effect/sex effect.

If the τ PK blood sample is collected slightly early (i.e., the 24 hours sample), the actual sampling time of the τ sample may be used for the calculation of $AUC_{0-\tau}$. However, the $AUC_{0-\tau}$ parameter will be calculated if the τ sample is within 60 minutes of the nominal sampling time.

8.5.1.3. Criteria for Handling Concentrations Below the Limit of Quantification or Missing Concentrations for Pharmacokinetic Analysis

Plasma concentrations below the limit of quantification (BLQ) will be assigned a value of 0 before the first measurable concentration and thereafter BLQ concentrations will be treated as missing. The following rules apply to the specific situations defined below:

- If an entire concentration-time profile is BLQ, it will be excluded from PK analysis.
- Where 2 or more consecutive concentrations are BLQ at the end of a profile, the profile will be deemed to have terminated and any further quantifiable concentrations will be set to missing for the calculation of the PK parameters, unless they are considered to be a true characteristic of the profile of the drug.
- If a predose plasma concentration is missing, it will be set to 0 by default within Phoenix WinNonlin for the first dosing day of all parts of the study.

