- For multiple dose part of the study (Day 14), if the analyte concentration at τ (24 hours postdose) is missing, this may be substituted with the predose concentration. Similarly, if the predose concentration is missing then this may be substituted with the concentration at τ . The PK parameters from any such profile will be listed but excluded from descriptive statistics and statistical analysis.

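### Any quantifiable predose value on the first dosing day, however small, removes that profile from every PK summary and model, while Part C Day 11 has no predose limit at all

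*SAP*

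**What the plan says.** SAP 8.5.1.4 (Treatment of Outliers) states: "Any quantifiable predose concentration value on the first dosing day of all parts of the study will be considered treated as 0". The consequence follows in its next sentence: "The PK parameters from any such profile will be listed but excluded from descriptive statistics and statistical analysis". No concentration limit or fraction of Cmax is attached. The paragraph before it lets an anomalous value be left out only with strong justification, documented in the CSR.

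The neighbouring rules do not reach Part C Day 11:
- For a missing predose value, SAP 8.5.1.3 says "it will be set to 0 by default within Phoenix WinNonlin for the first dosing day of all parts of the study".
- The substitution rule in the same section starts "For multiple dose part of the study (Day 14), if the analyte concentration at τ (24 hours postdose) is missing" and so concerns Part B.
- The interaction model in SAP 8.5.3.4 has treatment as a fixed effect and subject as a random effect, with no term for residual drug.

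The Part C schedule (Protocol 3.1.3, SAP 4.3) is "Days 1 and 11: single oral dose of KRP-A218", with two "single oral doses of 200 mg itraconazole, approximately 12 hours apart" on Day 4 and once-daily itraconazole afterwards. The interval before itraconazole may be lengthened according to the observed half-life, but no criterion is given.

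**The concern.** On a first dosing day nobody has yet received KRP-A218 (exclusion criterion 31 bars earlier receipt), so a trace predose reading is most likely assay noise or minor contamination. The rule still removes all of that profile's parameters from the statistics, whatever the size of the reading. Each Part A group has only six active subjects. One lost profile is a sixth of the group, and in the food or interaction comparison it breaks a within-subject pair.

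Part C Day 11 is a day on which true residual drug is possible, and its parameters are primary endpoints. There the SAP fixes no limit in advance. Handling would be left to the general anomalous-value clause and decided after the data are seen.

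**Working it through.** **Check of the decay model against the protocol.** Protocol Table 4 gives an accumulation ratio R of 1.6 from the 6 mg half-life of 16.9 h. R = 1/(1 − 2^(−24/16.9)) = 1.597, and 813 × 8/6 × 1.6 = 1734 against the stated 1730 ng·h/mL. Simple exponential decline therefore reproduces the plan's own figures.

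**Inputs (Protocol Table 3, fasted, geometric means at 1, 3 and 6 mg).** AUC0-∞ 210, 564, 1230 ng·h/mL; AUC0-tlast 198, 540, 1160 ng·h/mL; Cmax 11.9, 29.8, 60.3 ng/mL; half-life 18.2, 15.2, 16.9 h. CYP3A share 68.4% to 94.4% (Protocol 3.5). The means are treated as if from one subject.

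**How small a quantifiable value can be.** The assay limit is not given. The last quantified level at 1 mg is about (210 − 198) × ln2/18.2 = 0.46 ng/mL, so the limit is roughly that or lower. If 0.46 ng/mL were real drug declining at the usual rate, its area would be 0.46 × half-life/ln2:
- 6 mg: 11.2/1230 = 0.9% of AUC0-∞
- 3 mg: 10.1/564 = 1.8%
- 1 mg: 12.1/210 = 5.8%

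This is an upper bound. Contamination of the predose sample alone, set to 0, adds nothing.

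**Cost of losing the profile.** In a group summary the SE rises by √(6/5) = 1.095, about 10%. For paired comparisons the 90% CI factor is exp(t(0.95, n−1) × √(2 ln(1+CV²)/n)). The within-subject CV is not in the documents and is assumed:

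| Pairs | CV 10% | CV 20% | CV 30% |
|---|---|---|---|
| 6 (A2a) | 1.123 | 1.259 | 1.407 |
| 5 | 1.144 | 1.306 | 1.486 |
| 12 (Part C) | 1.076 | 1.156 | 1.240 |
| 11 | 1.080 | 1.165 | 1.255 |

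**Residue on Part C Day 11.** Take tlast as 72 h, when itraconazole starts, with 168 h from then to the second dose. Let f be the share of clearance blocked. The first dose then supplies this share of Day 11 AUC:

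[(AUC0-∞ − AUC0-tlast)/AUC0-∞] × 2^(−168(1−f)/half-life)

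- 6 mg, f = 0: 5.69% × 2^(−9.94) = about 0.01%
- 6 mg, f = 0.684: 5.69% × 2^(−3.14) = 0.65%
- 6 mg, f = 0.944: 5.69% × 2^(−0.56) = 3.9%
- 3 mg, f = 0.684 to 0.944: 0.4% to 2.8%
- 1 mg, f = 0.684 to 0.944: 0.8% to 4.0%

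At 6 mg the level at 72 h is 70 × ln2/16.9 = 2.87 ng/mL. The Day 11 predose level is then 0.33 to 1.95 ng/mL, or 0.5% to 3.2% of the Day 1 Cmax. A one-compartment simulation (half-life 16.9 h, tmax 3.5 h) gives 0.7% to 3.6% of the Day 11 Cmax and an AUC0-72 bias of 0.6% to 3.8%.

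**Slow eliminator.** Take a half-life one CV longer, using the 20.3% CV of the 3 mg fasted group: 16.9 × 1.203 = 20.3 h. At f = 0.944 the remaining fraction is about 2^(−(72 + 168 × 0.056)/20.3) = 2^(−4.01) = 6.2%. At f = 0.684 it is 2^(−(72 + 168 × 0.316)/20.3) = 1.4%. A 5% limit would therefore be passed only by slow eliminators near the top of the CYP3A range.

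**Cost of keeping a profile exactly at 5% of Cmax.** The area is 0.05 × Cmax × half-life/ln2, as a share of AUC0-∞: 73.5/1230 = 6.0% at 6 mg, 32.7/564 = 5.8% at 3 mg and 15.6/210 = 7.4% at 1 mg.

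**The case against.** The strongest defence concerns the first day. In a subject never given the drug, a quantifiable predose value cannot be carry-over. It may point to a sample mix-up or dosing error that puts the whole profile in doubt, so strict exclusion is a cautious choice. This stands in part: it is why larger values should still leave the primary analysis, and why the documented route for anomalous data should stay open below any threshold. It does not justify automatic exclusion of a trace reading in a section that asks for strong justification.

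Other points stand as well. The parameters are still listed, the unpaired Day 11 observation remains in the Part C model, and nothing shows how often such values occur. SAP 8.5.2 lists every concentration, so a Day 11 predose value would be visible, and the interval before itraconazole can be lengthened.

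A reader might infer that setting the value to 0 and then excluding the profile is self-contradictory. It is not: the zero determines how the listed parameters are calculated, and the exclusion governs the statistics.

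A reader might also extend the point to Period 2 of Group A2a. There the residue is negligible: 1.09 ng/mL at 72 h falls to 1.09 × 2^(−96/15.2) = 0.014 ng/mL at 7 days, about 0.05% of Cmax.

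**Conclusion.** The point holds as a minor one. The first-day rule discards usable parameters without regard to size, at a cost of about 10% in SE for a Part A group, or a CI factor of 1.31 instead of 1.26 in the food comparison at an assumed CV of 20%. The loss in Part C is smaller.

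For Day 11 the finding is a missing rule. A reader might infer that a large carry-over will distort the primary interaction ratio, but the documents do not support that. They nowhere say that residual drug is expected. It is an inference from the CYP3A share, the Day 4 start of itraconazole and the expected inhibition. With no inhibition, 240 h is about 14 half-lives. Under full block the typical bias is about 0.6% to 4%, while exposure itself would rise by 1/(1 − f), or 3.2-fold to 18-fold. Slow eliminators could exceed 5%.

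These sizes rest on exponential decline, tlast at 72 h, geometric means standing for one subject, and an unknown Part C dose and assay limit.

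**What to change.** Amend SAP 8.5.1.4 before unblinding and database lock.

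- **First dosing day (Part A, Part B Day 1, Part C Day 1).** If predose is at or below 5% of that profile's Cmax, keep the profile in all statistics. If it is above 5%, list it, exclude it from the primary analysis and show a sensitivity analysis that includes it.
- **Part C Day 11.** Keep all profiles in the primary interaction analysis and flag any predose above 5% of Cmax. Add a sensitivity analysis that either subtracts the extrapolated residual or omits the flagged profiles. They should not be excluded automatically: that would remove the slowest-clearing, most strongly inhibited of 12 subjects and pull the ratio down.

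The 5% limit is proposed here and has no source in the documents; what matters is that some limit is fixed in advance. The change is wording plus one or two extra tables. Its downside is that a profile with trace contamination is retained, worth roughly 6% to 7% of AUC0-∞ at most.

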8.5.2. Presentation of Pharmacokinetic Data

All PK concentrations and parameters will be listed.

Summary tables, arithmetic mean (+ standard deviation [SD]) figures, overlaying individual figures, and individual figures by treatment and time postdose will be provided for plasma

PK concentrations. All figures will be produced on both linear-linear and linear-logarithmic scales. The +SD bars will only be displayed on the linear-linear scale.

Summary tables by treatment will be provided for all PK parameters, with the exception of diagnostic regression-related PK parameters.

A subject may be excluded from the PK summary statistics and statistical analysis if the subject has an AE of vomiting that occurs at or before 2 times the median t_{max} .

If the actual time of sample collection deviates from the nominal time by more than $\pm 10\%$, the plasma/serum/whole blood concentration will be flagged and excluded from the summary statistics. Individual concentrations deemed to be anomalous will be flagged in the listings and excluded from the summary statistics.

For plasma/serum/whole blood concentration data, the following rules will apply:

- Values that are BLQ will be set to 0 for the calculation of summary statistics.
- Arithmetic mean or median values that are BLQ will be presented as 0.

For PK parameters, the following rule will apply:

- Geometric mean and coefficient of variation (CV) will not be calculated for t_{max} .

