3.4. Discussion of Study Design, Including the Choice of Control Groups

For Parts A and B of the study, a sequential-group, ascending dose design has been chosen for safety reasons as KRP-A218 is in the early stages of clinical development, with Part A of the study being the first time it will be administered to humans. Oral doses have been chosen for each part of the study, as this is the intended clinical route of administration. A 2-period design has been chosen for the food-effect arm, as this gives a within subject assessment of the influence of food on the PK of **CCI** [REDACTED] and so increases the power of the study for the given number of subjects.

It is the intent of Part B to dose subjects such that steady state plasma levels of **CCI** [REDACTED] are achieved and maintained for several days. Based on the available nonclinical data, it is expected that this will be achieved following 3 days of once daily dosing; however, a full review of all the available safety, tolerability, and PK data from Part A will be performed to confirm the dose regimen for Part B. If the $t_{1/2}$ of **CCI** [REDACTED] is longer than predicted by the nonclinical data, once-daily dosing may be more appropriate over 14 days (as steady state will take longer to achieve). The dose regimen will comprise no less than once every 3 days and will not exceed 3-times daily dosing. The dosing duration will not exceed 14 consecutive days of dosing.

Details of the dosing regimen and duration used for Part B of the study will be documented in the TMF. An interval of 7 to 10 days between doses of KRP-A218 in the food-effect arm in Part A is considered adequate to prevent carryover of KRP-A218 but the interval may be extended depending on the observed $t_{1/2}$ of **CCI** [REDACTED]

Parts A and B will be double-blind and placebo-controlled in order to avoid bias in the collection and evaluation of data during its conduct. Placebo has been chosen as the control treatment to assess whether any observed effects are treatment related or simply reflect the study conditions.

Continuous 12-lead ECG monitoring will be included in this study in order to explore potential KRP-A218 effects on the QT interval, with a view of supporting a potential thorough QT study waiver.

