^k To be recorded after the subject has been supine and at rest for at least 5 minutes.

^l Full physical examination.

^m Symptom-directed physical examination.

ⁿ Prior to discharge.

^o To be performed at approximately the same time as on Day 1.

^p Subjects will receive the IMP at the same time as Day 1 in Treatment Period 1 and 30 minutes after starting a high-fat breakfast.

^q If the latest result during the treatment period is positive, faecal samples will be collected for faecal occult blood test at the follow-up visit (within -2 day), as far as possible.

^r The interval between dosing is up to and including Day -1 of Treatment Period 2. The washout and follow-up periods may be extended depending on the observed $t_{1/2}$ of CCI

Table 11: Schedule of Assessments-Part B (Multiple-Dose) [Screening to Day 1]

Day	Screening	Treatment Period													
		-28 to -2	-1	Pre	0	0.25	0.5	0.75	1	1.5	2	3	4	6	8
Time Postdose(h)															
Informed consent	X														
Inclusion/exclusion criteria	X	X													
Demographic data	X														
Medical history	X	X ^a													
Urinary drug and cotinine screen	X	X													
Alcohol breath test	X	X													
Scrology	X														
Height	X														
IMP administration															
KRP-A218 or placebo ^b				X ^c											
Pharmacokinetics															
Blood sampling for the PK of CCI			X		X	X	X	X	X	X	X	X	X	X	X
Exploratory analyses															
Blood sampling for metabolite profiling ^d			X												
Urine collection for metabolite profiling ^{d,e}			<----X---->												
Pharmacogenetics			X												
Safety and tolerability															
Adverse event recording			<----->												
Prior/concomitant medication monitoring			<----->												
Body weight	X	X													
Haematology, clinical chemistry, coagulation, and urinalysis ^f	X	X													
Faecal occult blood test ^g	X	<----X---->		<-----X----->											
Bristol Stool Chart ^h		<----X---->		<-----X----->											
Blood pressure and pulse rate, and respiratory rate ⁱ	X	X	X ^j					X				X		X	X
Oral body temperature	X	X	X												
12-lead ECG for safety assessment ^k	X	X	X ^j					X				X		X	X
Physical examination			X ^l												
Abdominal examination			X								X				

Table 11: Schedule of Assessments-Part B (Multiple-Dose) [Day 2 to Day 13]

Day	Treatment Period											
	2	3	4	5	6	7	8	9	10	11	12	13
Time Postdose(h)	24	48	72	96	120	144	168	192	216	240	264	288
IMP administration												

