^a Interim medical history.^b Subjects will receive the IMP once daily at the same time as Day 1 in the fasted state (at least 10 hours).^c Subjects will be fasted until 4 hours after dosing, after which time a meal will be provided.^d Collected in Group B1 only.^e Spot urine sample will be collected any time prior to dosing. 24-hour urine samples will be collected on 0 to 24 hours postdose on Day 14.^f Subjects will be fasted at least 6 hours before collection.

^g Faecal occult blood test will be performed once each during the following sampling periods: Screening, Day -1 to prior to dosing, 0 to 24, 24 to 96, 96 to 168, 168 to 240 hours postdose on Day 1, 240 hours postdose on Day 1 to 0 hours on Day 14, and 0 to 72 hours postdose on Day 14. On screening, faecal samples will be collected to confirm eligibility for enrollment. For the other sampling periods, faecal samples will be collected as far as possible.

^h To be assessed when collecting faecal samples for faecal occult blood test in the treatment period.

ⁱ Subjects should be supine for at least 5 minutes before blood pressure and pulse rate measurements.

^j To be measured in triplicate at approximately 2-minute intervals.

^k To be recorded after the subject has been supine and at rest for at least 5 minutes.

^l Full physical examination.

^m Symptom-directed physical examination.

ⁿ Immediately before dosing.

^o From waking-up to before dosing.

^p To be performed at approximately the same time as on Day 1.

^q From waking-up to before breakfast.

^r If the latest result during the treatment period is positive, faecal samples will be collected for faecal occult blood test at the follow-up visit (within -2 day), as far as possible.

^s Prior to discharge.

^t The follow-up period may be extended depending on the observed $t_{1/2}$ of **CCI**

Table 12: Schedule of Assessments-Part C (DDI) [Screening to Day4]

Day	Screening	Treatment Period 1																
		-28 to -2	-1	1	2	3	4	6	8	12	24	36	48	72				
Time Postdose (h)		Pre	0	0.25	0.5	0.75	1	1.5	2	3	4	6	8	12	24	36	48	72
Informed consent	X																	
Inclusion/exclusion criteria	X	X																
Demographic data	X																	
Medical history	X	X ^a																
Urinary drug and cotinine screen	X	X																
Alcohol breath test	X	X																
Serology	X																	
Height	X																	
KRP-A218 and itraconazole administration^r																		
KRP-A218			X ^b															

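### The 10%-of-nominal-time filter in SAP 8.5.2 is too tight for early samples, undefined at predose, and loose enough for a postdose sample to be summarised as a Part B trough

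*SAP*

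**What the plan says.** SAP 8.5.2 gives one timing rule for all concentration data. "If the actual time of sample collection deviates from the nominal time by more than" 10% either way, the "concentration will be flagged and excluded from the summary statistics". No minimum or maximum width in minutes is given, and predose and trough samples are not mentioned.

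In Protocol Appendix 6, Table 11, the Part B samples on Days 2 to 13 sit under the header "Time Postdose(h) 24 48 72 96 120 144 168 192 216 240 264 288", although dosing is daily. A footnote on faecal sampling in the same table refers to "240 hours postdose on Day 1 to 0 hours on Day 14", so the hours in that table run from the Day 1 dose. Footnote n reads "Immediately before dosing". The marker on the Day 2 to 13 PK row comes through the text extraction as *a*, which is the interim medical history footnote. I take it to be *n*.

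Protocol 3.4 explains why these samples matter: "It is the intent of Part B to dose subjects such that steady state plasma levels" are reached and then held for several days. The SAP plans no formal test of steady state.

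SAP 8.5.1.2 has a different tolerance for the 24 h sample that closes the dosing interval: AUC0-τ is calculated if that sample lies within 60 minutes of nominal. SAP 8.5.1 derives PK parameters from actual sampling times.

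**The concern.** A tolerance proportional to nominal time behaves badly at both ends of this schedule. Just after dosing it is so narrow that a short delay removes a usable value. In Part B, if nominal time accumulates from Day 1, it widens every day while the quantity measured, the concentration just before the next dose, stays equally sensitive to timing. What matters for a trough is whether it was drawn before that day's dose and how close to it. The rule tests neither.

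At stake are the daily predose means in Part B. They are the only group-level numerical summary in the SAP of the approach to steady state. A postdose value averaged into them could mimic or hide a change of the size a reader is looking for.

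**Working it through.** **1. Width of the window.** Width = 0.10 × nominal time. The documents state no widths to compare with.

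| Sample | Nominal | Tolerance |
|---|---|---|
| Early | 0.25 h | ±1.5 min |
| Early | 0.5 h | ±3 min |
| Early | 1 h | ±6 min |
| Labelled Pre | 0 h | 0 or undefined |
| Part B Day 2 | 24 h | ±2.4 h |
| Part B Day 3 | 48 h | ±4.8 h |
| Part B Day 6 | 120 h | ±12 h |
| Part B Day 11 | 240 h | ±24 h |
| Part B Day 13 | 288 h | ±28.8 h |

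A 15-minute sample drawn 2 minutes late is 2/15 = 13.3% off and is excluded. On the Table 11 hours, the window from Day 3 (4.8 h) covers the median tmax of 3.0 to 3.5 h after that day's dose. From Day 11 it covers a whole dosing interval.

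**2. Alternative readings of nominal time for troughs.** Counted from the previous dose, nominal is 24 h every day and the tolerance is ±2.4 h, which still runs past the dose. Coded as predose, as the Part B Day 14 sample is, 10% of 0 is 0: either every sample properly drawn before the dose is excluded or the rule cannot be applied. The 60-minute tolerance in SAP 8.5.1.2 compares with 0.10 × 24 × 60 = 144 minutes here for a sample at 24 h.

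**3. Size of the effect, 6 mg fasted (Protocol Table 3).** Inputs: t1/2 16.9 h, Cmax 60.3 ng/mL, AUC0-24h 813 and AUC0-∞ 1230 ng·h/mL, median tmax 3.5 h. Part B has 8 active subjects per group (Protocol 3.1.2).

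- Rate constant: k = ln 2 / 16.9 = 0.0410 per h.
- Check against the plan: R = 1/(1 − exp(−24k)) = 1.597, against 1.6 in Protocol Table 4. For 8 mg, 813 × 8/6 × 1.597 ≈ 1731, against the stated 1730.
- Concentration at 24 h: (1230 − 813) × 0.0410 ≈ 17.1 ng/mL.
- Steady-state trough: 17.1 × 1.597 ≈ 27.3 ng/mL.
- Steady state, 3.5 h postdose, by linear superposition: 60.3 + 27.3 × exp(−3.5k) ≈ 84.0 ng/mL.
- Ratio to trough: 84.0 / 27.3 ≈ 3.1.
- Day mean with one such value among 8: (7 + 3.07)/8 ≈ 1.26, a rise of about 26%.

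The same steps give 3.3-fold and 29% from the 3 mg fasted data, and 3.8-fold and 34% from the 1 mg data.

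**4. Against the change being looked for.** The fraction of steady state in the predose sample after n doses is 1 − exp(−24kn): 63% on Day 2, 86% on Day 3, 95% on Day 4 and 98% on Day 5. From Day 4 onward only about 5% of the rise remains.

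**5. A 60-minute predose window.** A trough drawn 60 minutes early is inflated by exp(0.0410 × 1) = 1.042, about 4%.

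**6. Loss of a mean.** SAP 8.1.2 withholds most statistics when n < 3. That needs 4 of 6 values excluded at one timepoint in Part A (6 − 4 = 2), or 6 of 8 in Part B (8 − 6 = 2).

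**The case against.** A reader might infer that the filter corrupts the only view of steady state, or the Part B PK results. The documents do not support that. The exclusion applies to summary statistics. SAP 8.5.2 still lists every concentration and plans overlaid and single-subject figures. AUC, Cmax, half-life, the accumulation ratios and the model-based comparisons rest on actual times. The accumulation ratios also bear on steady state and can be set against the predicted R of 1.6. All of this stands, and it limits the point to summary tables and mean figures.

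Nor do the documents suggest that mistimed troughs are likely. Subjects are resident from Day -1 to the morning of Day 17 (Protocol 3.1.2), dosing is supervised (5.5), dosing and PK samples come first in scheduling (section 7), and footnote n requires a predose draw. Deviations are considered before database lock (SAP section 7), and anomalous concentrations may be excluded (8.5.2). This stands as to frequency. The last two safeguards depend on judgement, however, and do not define an acceptable trough.

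The 28.8 h figure depends on taking the Table 11 hours as nominal times. That is the literal reading, but the SAP does not confirm it. Counted from the previous dose, a 3.5 h postdose sample would be rejected, so the 26% illustration would not apply as it stands. A sample up to 2.4 h after the dose would still pass, and individual tmax at 6 mg ranged from 1.50 to 4.00 h, so for some subjects that includes the peak.

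It is also tempting to read the 1.5-minute window as a routine loss of early means. No document gives a rate of late samples, four of six Part A values would have to go, and the 0.25 to 0.75 h samples precede the median tmax by more than two hours. The usual cost would be a smaller n. Collection procedures are in a separate document (Protocol 7.1.1), which may set its own windows.

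**Conclusion.** The point holds as a minor defect in a stated rule. No single reading of nominal time makes the 10% rule work across the schedule: it gives ±1.5 minutes at 0.25 h, nothing usable at predose, and for Part B troughs either ±2.4 h or up to ±28.8 h. Both trough readings admit postdose samples, and both are wider than the SAP's own 60 minutes.

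The effect is confined to concentration summary tables and mean figures. Where a sample 3.5 h postdose is accepted, one among eight would raise that day's mean trough by about 26% (26% to 34% across the 1 to 6 mg data), more than the roughly 5% of the rise still to come from Day 4. These figures assume linear superposition, log-linear decline after 24 h and the preliminary Part A values. Part B doses are not stated. Nothing in the documents shows that such samples will occur, and no conclusion about PK parameters, accumulation or dose proportionality is affected.

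**What to change.** Replace the single rule in SAP 8.5.2 with the following:

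- **Part B predose samples, Days 2 to 14:** measure against the current day's dose. Include in summaries only if drawn before that dose and within 60 minutes of it, in line with SAP 8.5.1.2.
- **Other samples labelled Pre, and the Part C Day 4 72 h sample:** apply the same predose condition. Footnote e of Protocol Table 12 already asks for the 72 h sample before dosing, but the present rule would accept it up to 7.2 h late, after itraconazole has started.
- **Postdose samples up to 1 h:** an absolute window in minutes, set by the sponsor.
- **Later samples:** 10% of the time since the most recent dose of the drug being measured, capped at 60 minutes up to 24 h.

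Listings should continue to show every value with its flag. The cost is SAP wording and one derived variable, time since the most recent dose. No new data are needed.
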